|                    | 
 
Percentage of subjects achieving remission. Remission is defined as a score of ≤ 3 on each of the following specific PANSS items: delusions (P1), unusual thought content (G9), hallucinatory behavior (P3), conceptual disorganization (P2), mannerisms/posturing (G5), blunted affect (N1), passive/apathetic social withdrawal (N4), and loak of spontaneity and conversation flow (N6).
 
   |  |
|                    | 
 
Change in the CGAS Score
 
  |  |

|                      | 
 
Change in the Clinical Global Impression Severity (CGI-S) scale
 
Clinical Global Impression Improvement (CGI-I) scale
 
  |
|----------------------|--|
|                      | Safety will be assessed by the following:  |
|                      | • The frequency and severity of AEs, serious AEs (clinical and laboratory), and discontinuation from the trial due to AEs  |
|                      | • Weight, height, body mass index, and waist circumference   |
|                      | 
 
Analysis of potential suicide events recorded on the
C-SSRS
 
  |
|                      | • Clinical laboratory tests and urinalysis results (including serum prolactin), vital signs, and ECG parameters  |
|                      | • Changes on the SAS, AIMS, and BARS   |
|                      | • Comprehensive psychotropic side effects as assessed by the UKU side effect rating scale  |
|                      | • Cognitive adverse effects as assessed by the NY-AACENT   |
| Statistical Methods: | Based on the results of the aripiprazole trial conducted in
adolescent subjects with schizophrenia (Protocol 31-03-239),
aripiprazole 30 mg and 10 mg had a reduction in PANSS
Total Score of 7.40 and 5.46, respectively, compared to
placebo. The standard deviation (SD) at Week 6 was 19.
Assuming that brexpiprazole 2–4 mg has comparable
treatment effects to aripiprazole 30 mg, as well as the same
SD, a sample size of 105 subjects per arm will provide at least
80% power at a nominal 2-sided alpha level of 0.05 to detect a
-7.4 point reduction in PANSS Total score change from
baseline to Week 6 for brexpiprazole vs placebo assuming an
SD = 19. With 1:1:1 allocation ratio, the overall sample size of
this trial is planned to be 315 subjects. |

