# 2 Trial Rationale and Objectives

### 2.1 Trial Rationale

The onset of schizophrenia symptoms typically peaks in late adolescence and early adulthood; however, prodromal symptoms may be present for several years before the initial psychotic episode. In a minority of cases, the initial episode may occur during childhood or early adolescence. Patients who experience this "early-onset schizophrenia" tend to exhibit symptoms that are more severe and follow a more chronic course. Whereas adults with schizophrenia typically experience exacerbations of psychotic symptoms between periods of relative normalcy, adolescents with schizophrenia may never achieve full remission of the initial episode. The prognosis for early-onset schizophrenia to be poor; cognitive impairment is greater compared with individuals whose onset of schizophrenia occurs later in life. In addition, refinement of social interaction skills that takes place during the teen years is interrupted, leading to a reduced ability for successful function in adulthood. Several antipsychotics have been investigated for the treatment of adolescent schizophrenia. Management of these subjects presents a particular challenge because developing bodies are more sensitive to side effects of antipsychotics, particularly with respect to weight gain.

The current phase 3 trial is part of the brexpiprazole clinical development program that has been designed to demonstrate the efficacy and safety of brexpiprazole for the treatment of adolescents with schizophrenia. A 6-week double-blind treatment period is considered to be of adequate length to determine whether an antipsychotic effect has been demonstrated. Criteria for early termination (ET) from double-blind treatment will be determined by the investigator and corroborated with quantitative assessments. The aripriprazole arm proposed in this trial provides assay sensitivity.

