# 7 Statistical Analysis

#### 7.1 Sample Size

A sample size of 105 subjects per arm is considered adequate for this trial. It will provide at least 80% power at a nominal 2-sided alpha level of 0.05 to detect a -7.4-point reduction in PANSS Total Score change from baseline to Week 6 for brexpiprazole vs placebo assuming a standard deviation (SD) of 19. With a 1:1:1 allocation ratio, the overall sample size of this trial is planned to be 315 subjects. This will provide a sample size comparable to other similar trials.

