#### 7.4 Primary and Secondary Endpoint Analyses

#### 7.4.1 Primary Endpoint Analysis

The primary efficacy variable in this trial is the change from baseline to Week 6 in PANSS Total Score.

The primary estimand defining the treatment effect of interest in the protocol uses the hypothetical strategy specified in the International Council for Harmonisation (ICH) E9 Addendum. The objective of the primary analysis is to compare the efficacy of brexpiprazole versus placebo in adolescents with schizophrenia. The estimand, or target of estimation, following this hypothetical strategy is the treatment effect seen, assuming that no withdrawals occurred. Subjects who withdraw from IMP treatment either could have lost their treatment effect had the subjects not taken any other treatment after withdrawal or could have had their treatment effect masked had the subjects taken other treatment after withdrawal. This would mean that any observations made after subjects stop IMP will most likely not contribute relevant information about the treatment effect of the drug. Due to this strategy, the last efficacy assessment after premature trial discontinuation will be done only once at the ET Visit. Every effort will be made to complete all of the ET evaluations prior to administering any additional medications for the treatment of schizophrenia or other prohibited medications. In the case of terminal or lost to follow-up events, no ET evaluations would be expected, and only scheduled assessments would be performed before such an event occurred.

The primary estimand for this trial is defined by the following components:

- Target Population: Adolescent subjects 13 to 17 years of age with schizophrenia who met the protocol-defined inclusion/exclusion criteria and were qualified for the Efficacy Sample
- Endpoint: Change from Baseline to Week 6 in the PANSS Total Score
- Intercurrent Events: Refers to premature treatment discontinuation (ie, early dropout) prior to Week 6 attributable to adverse events, lack of efficacy, withdrawal of consent/assent, or any other causes
- Measure of Intervention Effect: Difference in endpoint means between the brexpiprazole arm and the placebo arm.

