In this hypothetical strategy, the event of withdrawing IMP is considered MAR, and the primary endpoint of the trial could be considered as a combination of the responses of on treatment completers at Week 6 and the imputation of the endpoint to Week 6 following the trend in each treatment group, using the MMRM method to impute missing data for

subjects who withdraw IMP during the trial. All data collected during the trial treatment period will be used for statistical analysis. For the primary efficacy analysis, the treatment effect will be estimated using the MMRM method described below. Under the MAR assumption, MMRM provides an unbiased estimate of treatment effect for the treatment period. Analyses with missing values imputed by MI under MNAR and other methods will be performed as sensitivity analyses.

The primary statistical comparison of interest is brexpiprazole 2–4 mg versus placebo. With the assumption of MAR, an MMRM analysis with fixed-effect factors of treatment, trial site, visit, treatment by visit interaction, and fixed effect covariates of baseline and baseline by visit interaction will be applied to the change from baseline from Week 1 to Week 6 in PANSS Total Score based on all available data (OC dataset). The data will be modeled using an unstructured variance covariance matrix for the within subject variation. A statistical test of the least squares (LS) mean differences at Week 6 of the MMRM analysis will serve as the analysis of the primary endpoint. The Efficacy Sample will be used in the analysis of the primary endpoint. The comparison will be tested at a significance level of 0.05 (2-side).

In case there is a convergence problem with the MMRM model with the unstructured variance covariance matrix, the following structures other than unstructured will be used in order of 1) heterogeneous toeplitz, 2) heterogeneous autoregressive of order 1, and 3) heterogeneous compound symmetry, and the first (co)variance structure converging to the best fit will be used as the primary analysis. If a structured covariance has to be used, the "sandwich" estimator of the standard error of the fixed effects parameters will be used in order to deal with possible model misspecification of the covariance matrix.

In order to explore the robustness of the primary analysis based on the MAR assumption, sensitivity analysis of the primary efficacy endpoint under the MNAR assumption will be conducted, using a pattern-mixture model.

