3.4 Trial Visit Window

Study visit windows will be used to map visits using study day intervals. This visit window convention applies to tables and listings for all efficacy and safety scales when presented by scheduled visit (PANSS, CGAS, CGI-S, CGI-I, CCI SAS, AIMS, BARS, NY-AACENT).

The scheduled visits for PANSS measurement and other scales assessments are Day 1 and Week 1, 2, 3, 4, 5, and 6, respectively. The first day of double-blind dosing is defined as "Day 1". A window of 2 days is allowed for week 1 to 6 per protocol. Trial Days are derived from the formula: Trial Day = Date of assessment - Date of first dose of IMP +1. Based on the trial days, observations are mapped to the corresponding week in the summary tables as per Table 3.4-1. If more than 1 observation falls within a particular study day interval, then the last observation within that interval is used. Evaluations occurring more than 7 days after the last double-blind dosing date will not be mapped into trial visit windows and will be excluded from the analysis.

Table 3.4-1	Time of Window for Mapping Visit	
Week	Target Day	Trial Day Interval
1	7	2 - 10
2	14	11 - 17
3	21	18 - 24
4	28	25 - 31
5	35	32 - 38
6	42	39 - 49 ^a

^aEvaluations occurring more than 7 days after the last dosing date of IMP in the double-blind treatment period will be excluded from the analyses.

4 Sample Size

A sample size of 105 subjects per arm will provide at least 80% power at a nominal 2-sided alpha level of 0.05 to detect a -7.4 point reduction in PANSS Total score change from baseline to Week 6 for brexpiprazole vs placebo assuming an SD of 19. With a

1:1:1 allocation ratio, the overall sample size of this trial is planned to be 315 subjects. This will provide a sample size comparable to other similar trials.^{1,2}

5 Statistical Analysis Datasets

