6.1.1 Primary Estimand

The primary clinical question of interest is: What is the intervention difference in change from baseline in PANSS after 6 weeks of treatment where no patient would discontinue treatment due to any reason.

The primary estimand is defined by the following components:

- **Population:** Adolescents (13 17 years old) with a primary diagnosis of Schizophrenia who would benefit from pharmacological treatment.
- Endpoint: Change from Baseline to Week 6 in the PANSS Total Score
- **Intercurrent Events:** Refers to premature treatment discontinuation (ie, early dropout) prior to Week 6 attributable to adverse events, lack of efficacy, withdrawal of consent/assent, or any other causes The intercurrent event will be handled through the hypothetical strategy.
- **Treatment condition:** one of the randomized treatment groups of the following per protocol: brexpiprazole, aripiprazole or placebo
- **Population-level summary**: Difference in endpoint means between the brexpiprazole arm and the placebo arm.

17

Rationale for estimand: hypothetical estimand justifiable to evaluate the pharmacological effect, had no withdrawals occurred. Subjects who withdraw from IMP treatment either could have lost their treatment effect had the subjects not taken any other treatment after withdrawal or could have had their treatment effect masked had the subjects taken other treatment after withdrawal. This would mean that any observations made after subjects stop IMP will most likely not contribute relevant information about the treatment effect of the drug. Due to this strategy, the last efficacy assessment after premature trial discontinuation will be assessed only once at the Early Termination (ET) Visit. Every effort will be made to complete all of the ET evaluations prior to administering any additional medications for the treatment of schizophrenia or other prohibited medications. In the case of terminal or lost to follow-up events, no ET evaluations would be expected, and only scheduled assessments would be performed before such an event occurred.

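### Does the assay-sensitivity role of the aripiprazole arm require the plan to name an aripiprazole-versus-placebo comparison?

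*Protocol*

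**What the plan says.** Protocol 2.1 gives the active arm its purpose in one sentence: "The aripriprazole arm proposed in this trial provides assay sensitivity". No analysis is attached to it there.

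Where a PANSS Total Score comparison names its arms, they are brexpiprazole and placebo:

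- Sample size, Protocol 7.1: "for brexpiprazole vs placebo assuming a standard deviation (SD) of 19". SAP Section 4 repeats it: "baseline to Week 6 for brexpiprazole vs placebo assuming an SD of 19".
- Estimand, Protocol 7.4.1: "Measure of Intervention Effect: Difference in endpoint means between the brexpiprazole arm and the placebo arm". The population-level summary in SAP 6.1.1 is the same: "Difference in endpoint means between the brexpiprazole arm and the placebo arm".
- Primary comparison, Protocol 7.4.1: "The primary statistical comparison of interest is brexpiprazole 2–4 mg versus placebo". SAP 8.1.1 and the text introducing the estimate statement in SAP 8.1.3.2 agree.

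Other text treats the analysis as three-arm. SAP 6.1.1 gives the treatment condition as "one of the randomized treatment groups of the following per protocol: brexpiprazole, aripiprazole or placebo". SAP 8.1 includes every randomized subject with baseline and post-baseline totals. The placebo-based imputation in SAP 8.1.2 covers aripiprazole subjects explicitly. SAP 8.1.4 (the treatment contrast) and SAP 8.2 (CGI-I differences between arms) promise estimates and intervals without saying which arms. The addendum of 21 Aug 2023 adds race and ethnicity analyses and leaves the methods as they were.

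**The concern.** A third of the planned 315 subjects (105) go to an arm whose stated purpose is assay sensitivity. Including the arm does not establish assay sensitivity; the aripiprazole-placebo difference observed in this trial does. A plan that states the purpose but never names the comparison seems to leave that purpose without an analysis.

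The worry is sharpest if brexpiprazole does not separate from placebo. A reader would then ask whether the trial could have detected an effective drug at all. The comparison that answers this would be one the visible plan had not listed, so it could be called post hoc, and its level and reading would be undeclared.

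**Working it through.** **1. The plan's own figure.** Inputs from Protocol 7.1: difference 7.4, SD 19, two-sided alpha 0.05, power at least 80%, 105 per arm.

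- n per arm = 2 × (1.960 + 0.842)² × 19² / 7.4² = 103.5, rounded up to 104.
- SE at 105 per arm = 19 × √(2/105) = 2.622.
- Power at 7.4: 7.4 / 2.622 = 2.822, giving 80.6% (normal) or 80.2% (noncentral t, 208 df).
- 3 × 105 = 315.

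The stated size reproduces. It was set for brexpiprazole versus placebo, and neither document claims power for aripiprazole versus placebo.

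**2. Precision of the unnamed contrast.** Allocation is 1:1:1, so under the same SD the SE is again 2.622. With t = 1.971, the half-width is 1.971 × 2.622 = 5.17 points.

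The Synopsis cites two aripiprazole effects from the previous adolescent trial, for 30 mg and 10 mg: "Total Score of 7.40 and 5.46, respectively, compared to" placebo. This trial's arm is flexible 10–20 mg, so neither figure estimates its effect; they serve as reference points. The midpoint, (7.40 + 5.46)/2 = 6.43, is an assumption.

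| Assumed effect | Power, 105 per arm | Power, 79 per arm |
|---|---|---|
| 5.46 | 54.5% | 43.5% |
| 6.43 | 68.5% | 56.1% |
| 7.40 | 80.2% | 68.2% |

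All entries are noncentral t, two-sided 0.05, SD 19. The last column assumes that 25% of Week 6 values are lost and the MMRM recovers nothing. The documents state no dropout rate. With losses of 10% or 20% (94 or 84 per arm), power at 5.46 is 50.0% or 45.7%, and the half-width is 5.47 or 5.79. An MMRM recovers part of the loss, so the real values lie between these and the complete-data values.

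**3. What an analyst still has to decide.** The items needed to produce the aripiprazole-placebo difference at Week 6, and where each is fixed:

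- Subjects: Efficacy Sample, SAP 5.4 and 8.1.
- Visit mapping and early-termination visits: SAP 3.4 and 8.1.3.
- Model terms, unstructured covariance, fallback order and degrees of freedom: SAP 8.1.1.
- Site pooling: SAP 8.1.3.1, which calls a site small unless it has an evaluable subject in each treatment arm.
- Contrast coefficients: the aripiprazole and placebo LS means at Week 6 from the same treatment-by-visit term.

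Only the last is not spelled out in visible prose, and given the question it has one answer. Two analysts working independently would get the same estimate and interval.

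**4. What depends on it.** The primary test is a single contrast at two-sided 0.05. A supportive aripiprazole-placebo estimate takes no alpha from it and does not enter the primary decision.

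**The case for a change.** The strongest case for a change is that the gap is real and cheap to close. It would take one SAP sentence and at most one estimate statement, with no alpha, subjects or protocol amendment involved. A comparison declared before unblinding carries more weight than one first shown afterwards. Limited precision also makes it useful to say in advance that non-separation of aripiprazole alone would not settle the question. The generic phrases in SAP 8.1.4 and 8.2 name no arms, and calling one comparison primary does not plan any other.

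The literal gap stands: no visible sentence names the contrast. The consequence is weaker. The arm's role was declared in the protocol, so examining it against placebo on the primary endpoint would not be a question invented after the data. The model was fixed for all three arms, which removes the choices that normally make an unlisted comparison suspect. The code block where the contrast would most naturally appear cannot be seen, so its absence is not established. Low power at 5.46 is only one end of the range, and it follows from the sample size; naming the contrast leaves it unchanged. The visible text gives no database-lock or unblinding date, so it is not known whether an addition before unblinding is still possible.

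**Conclusion.** No change to the plan is called for. This is missing detail that analysts would fill in one way: the aripiprazole-placebo LS-mean difference at Week 6, with its 95% interval, from the model already specified. No stated rule gives a wrong result, and the primary estimate, its alpha and its conclusion are untouched. A labelling sentence would do no harm, but nothing in the analysis turns on it.

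The comparison would be supportive whether named or not, with a half-width of about 5.2 points under complete data and power of about 55% to 80% over the two cited effects. This rests on three assumptions: SD 19 also applies to the aripiprazole arm; dropout is unknown, so precision may be somewhat worse; and the unseen SAS statements do not contradict the three-arm model described in the prose.

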### 2.2 Dosing Rationale

Brexpiprazole has been well tolerated at multiple oral doses up to 12 mg/day in adult subjects with schizophrenia or schizoaffective disorders. A dose range of 0.25 to 6 mg/day was investigated in a phase 2 trial in adults with schizophrenia. The safety, tolerability, and PK of brexpiprazole have been studied in healthy adult subjects and patients (18 years and older), including those with schizophrenia or schizoaffective disorder. A PK, safety, and tolerability trial in adolescent (13–17 years old) subjects with a diagnosis of schizophrenia or other related psychiatric disorders (ie, bipolar disorder) was completed (Trial 331-10-233). Subjects who were deemed eligible for

Trial 331-10-233 were assigned to a dosing cohort and entered a Dose Titration Phase during which they received a starting dose of brexpiprazole (0.5 mg or 1 mg) for 2 to 10 days based on their assigned titration schedule. Following the Dose Titration Phase, subjects entered the Fixed Dose Phase and were administered the assigned dose (0.5 mg to 4 mg) for that cohort for 14 days. For the final Cohort a Dose Titration of 1 mg on Days 1 and 2; 2 mg on Days 3 and 4; 2.5 mg on Days 5 and 6; 3 mg on Days 7 and 8; and 3.5 mg on Days 9 and 10, followed by 4 mg daily for 14 days was followed. Brexpiprazole at doses of 0.5 mg/day, 1 mg/day, 2 mg/day, 3 mg/day, and 4 mg/day was generally safe and well tolerated in adolescent subjects with schizophrenia, bipolar disorder, or other related psychiatric disorders. Overall, systemic exposure and apparent clearance did not appear to be significantly different between adolescent and adult subjects while high variability due to limited number of evaluable subjects contributed to small differences between the PK evaluable and PK populations.

Based on results of pivotal safety and efficacy in adult patients with schizophrenia, a dose range of 2 to 4 mg is shown to be efficacious (Rexulti Label). Based on the safety and PK data in Trial 331-10-233, no dose adjustment is deemed necessary in children and adolescents and thus a similar efficacious dose range of 2 to 4 mg is proposed for this trial. In adult patients, brexpiprazole is initiated as 1 mg for 3 days followed by 2 mg for 3 days, and a similar dose initiation is proposed in adolescent patients as a similar dose initiation scheme was evaluated in the final cohort of Trial 331-10-233 with no safety or tolerability concerns.

## 2.3 Trial Objectives

The objective of the trial is to evaluate the short-term efficacy and safety of brexpiprazole monotherapy in the treatment of adolescents with schizophrenia.

# 3 Trial Design

## 3.1 Type/Design of Trial

This is a multicenter, randomized, double-blind, placebo- and active-controlled trial designed to assess the effect of brexpiprazole compared to placebo in adolescent subjects, ages 13 to 17 years at the time of informed consent/assent and at baseline (Day 1), with a *Diagnostic and Statistical Manual of Mental Disorders - Fifth Edition* (DSM-5) diagnosis of schizophrenia. The initial diagnosis of schizophrenia should be made by an adequately trained clinician (psychiatrist or local medical equivalent who is experienced in treating adolescents with schizophrenia). The diagnosis should then be confirmed by utilizing the Kiddie Schedule for Affective Disorders and Schizophrenia-Present and

Lifetime version (K-SADS-PL), performed by an adequately trained rater at the time of screening. The trial is planned to be conducted on an outpatient basis. Any hospitalization needed for prospective subjects, such as hospitalization needed to allow subjects to change medications in preparation for this trial requires discussion with the Medical Advisor.

This trial has a 6-week treatment double-blind period.

After a minimum 3-day washout period, subjects who continue to meet all entrance criteria (including Positive and Negative Syndrome Scale [PANSS] Total Score  $\geq$  80) at the baseline visit (Day 1) will be randomized 1:1:1 to 1 of 3 double-blind treatment arms:

- 2-4 mg brexpiprazole daily
- 10-20 mg aripiprazole daily
- Placebo

Brexpiprazole will be titrated to the minimum target dose of 2 mg in 8 days and aripiprazole will be titrated to the appropriate therapeutic dose consistent with the US package insert (minimum dose of 10 mg). Subjects who are unable to tolerate the minimum target dose will be discontinued. At the end of the titration period, investigators will be able to adjust the dose of double-blind IMP not to exceed 4 mg/day in the brexpiprazole treatment arm or 20 mg/day in the aripiprazole treatment arm. If subjects are not able to tolerate the minimum dose, they will be discontinued from the trial.

During the double-blind treatment phase, mandatory evaluations will take place at Day 1 (baseline), Day 4 (telephone call), and Weeks 1, 2, 3, 4, 5, and 6. However, at the discretion of the treating physician, more frequent evaluations are permitted. Data collected from subjects undergoing ad hoc evaluations may be excluded from efficacy analysis.

Eligible subjects who complete the trial may have the option to enroll into an open-label safety trial of brexpiprazole (Protocol 331-10-236). All subjects who do not enroll in the open label rollover trial (Protocol 331-10-236) will be assessed either via site visit or telephone assessment 21 ( $\pm$  2) days after the last dose of IMP to assess adverse events (AEs).

A schematic of the trial design is shown in Figure 3.1-1.

Confidential - Proprietary Information

32

Version 5.0, 05 Jul 2022

Until the information herein is released by Otsuka to the public domain, the contents of this document are Otsuka confidential information and should not be duplicated or re-distributed without prior written consent of Otsuka.

